#### 2.3.1.1 (For arms in the ARVs without TB Treatment study arm group)

Objective:

To describe the pharmacokinetic parameters during pregnancy of selected ARV drugs currently used in the clinical care of HIV-infected pregnant women, and to compare these parameters to a) historical pharmacokinetic data from non-pregnant women and b) postpartum pharmacokinetic data from the same women in the study cohorts.

Outcome measure: a) # of women who met area under the curve (AUC) target of ARVs in 2nd trimester (2T), 3rd trimester (3T) and postpartum (PP) (see PK target in Protocol Appendix V); b) AUC, Cmax and Ctrough of ARVs in 2T, 3T and PP

**2.3.1.2 (For arms in the ARVs with First Line TB Treatment arms or No ARVs with First Line TB Treatment study arm groups)**

Objective:

To describe the pharmacokinetic parameters during pregnancy and postpartum of selected ARV drugs (efavirenz, lopinavir/ritonavir) and first line TB drugs when co-administered as part of clinical care of HIV-infected pregnant women and of first line TB drugs when used in HIV-uninfected pregnant women.

Outcome measure: a) # of women who met the AUC target for ARVs and the  $C_{max}$  target for first line TB drugs in 2T, 3T and PP (see PK targets in Protocol Appendix V); b) ARV and first line TB drug AUC,  $C_{max}$  and  $C_{trough}$  in 2T, 3T and PP

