### 3 General Considerations

Each analysis will include all participants with evaluable data for that analysis. A participant's data will be deemed unevaluable by a protocol pharmacologist for a specific analysis if they do not have adequate pharmacokinetic evaluations to determine the pharmacokinetic exposure parameter of interest for that analysis. For safety analyses, a participant's data will be deemed unevaluable only if the participant did not receive any amount of the drug under study.

Visit windows are defined in Protocol Appendix IA-ID and Appendix II for mothers and infants, respectively. Specifically, maternal HIV RNA and CD4 tests for each PK visit allow a window of  $\pm$  8 weeks around the PK evaluation date. For mothers of non-contraceptive arms, entry visit (which may occur at the 2P or 3P visit) is the baseline; for mothers of contraceptive arms, entry visit (2-12 weeks postpartum) is the baseline. For infants, day of birth is defined as Day 0; birth visit is the baseline.

Continuous variables (e.g. gestational age) will be summarized with descriptive statistics (mean, median, standard deviation, interquartile range, and range). Categorical data (e.g. sex) will be summarized with frequencies and percentages for each category. Reports may also include listings with details related to safety events.

In this study, each arm will enroll independently. Final analysis for each arm will be done when that arm completes follow-up and PK assays have been run. Each study arm will have a separate Final Analysis Report (unless the team decides to combine analyses across certain arms).

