### 4 Analysis Approaches

For the PK related objectives, this SAP defines the descriptive PK data summaries and PK comparisons to be done by the protocol statisticians. The pharmacokinetic parameters will be calculated by the protocol pharmacologists, and their derivation/analysis will be defined in a separate Pharmacokinetic SAP.

If PK concentration values are missing due to below the level of quantification (BLQ), they will be set to  $\frac{1}{2}$  the lower limit of quantitation (LLOQ) for calculations. If an entire concentration-time profile is BLQ, the profile will be reported separately and excluded from the summary PK analysis. The comparisons to be performed to address the primary objectives for certain arms will vary according to type of drug and timing of sampling. Table 1 summarizes these comparisons for each type of drug.

Table 1: Pharmacokinetic Parameter Comparisons to be Performed for Each Type of Drug for the Primary Objectives

Type of Drug	Analysis Stage	Description of Pharmacokinetic Parameter Comparison	Type of Comparison
ARV without TB Drugs	Stage 1	Antepartum PK parameter vs. 10 th percentile from external, non-pregnant population	Between-participant
	Stage 2	Antepartum vs. postpartum PK parameters	Within-participant
ARV with First Line TB Drugs	Stage 1	Antepartum ARV PK parameter vs. 10 th percentile from non-pregnant population	Between-participant
	Stage 2	Antepartum vs. postpartum ARV PK parameters	Within-participant
	Stage 3	ARV PK parameter with TB drugs vs. ARV PK parameter without TB drugs in previous P1026s arm	Between-participant
First Line TB drugs with ARVs (HIV+) and First Line TB drugs without ARVs (HIV-)	Stage 1*	Antepartum TB drug PK parameter vs. 10 th percentile from non-pregnant population	Between-participant
	Stage 2	Antepartum vs. postpartum TB drug PK parameter, separately for HIV+ and HIV-	Within-participant**
	Stage 3	TB drug PK parameter with ARV (HIV+) vs. TB drug PK parameter without ARV (HIV-)	Between-participant
Second Line TB drugs with or without ARVs	Stage 2	Antepartum vs. postpartum TB drug PK parameters	Within-participant**
ARV with Contraceptives #	Stage 2	Postpartum ARV PK parameter before vs. after starting contraceptives	Within-participant
Contraceptives with ARVs	Stage 3	Postpartum contraceptive concentration with ARV vs. external historical controls not receiving ARV	Between-participant

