
*Stage 1 analysis for the TB drugs will not be done in real time and will only be done when batched PK data are available (unlike the Stage I analysis for ARVs).  **This comparison may have a smaller sample size than 25 because some women may complete their TB treatment before the postpartum PK visit.  #Interim AUC monitoring (Stage 1 analysis) is not done for these arms (only done during pregnancy).
			

In Stage 1, an individual woman’s PK exposure parameter during pregnancy will be compared in real time to the 10th percentile for that PK exposure parameter for that drug from a non-pregnant population, and the woman and her clinical provider will be notified if the woman’s value is below the 10th percentile. If there is strong evidence that the true percentage of pregnant women having the PK exposure parameter below the 10th percentile for the non-pregnant population is greater than 10%, the study team will evaluate whether to stop enrollment early and whether to recommend that additional study of the drug/drug combination is necessary.

Stage 2 for the ARV drugs taken during pregnancy will implement a repeated measures design, in which antepartum and postpartum measurements from each woman will be compared. This stage requires a minimum of 12 participants in each arm to have postpartum PK measurements. If less than 12 participants out of the 25 in any arm have postpartum measurements, more participants will be enrolled in that arm until the minimum postpartum measurement number of 12

is reached. The comparisons will be made at the within-participant level, using the Wilcoxon signed rank test to assess whether there is a statistically significant difference in the PK exposure parameter in the pregnant versus non-pregnant conditions. 90% confidence limits for the geometric mean ratio of the PK exposure parameter in the pregnant versus non-pregnant conditions will also be calculated to describe the range of values that are consistent with the observed data and help the Protocol Team assess whether there is a clinically important difference in exposure in the pregnant versus non-pregnant conditions.

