For the ARV drugs being taken with first line TB drugs, in addition to Stages 1 and 2, a third stage of analysis (Stage 3) will be performed which will compare the ARV PK exposure with first line TB drugs to the PK exposure for these ARVs without first line TB drugs in previously evaluated arms of the P1026s study. This analysis will involve a between-participants comparison of PK exposure parameters using the two-sample Wilcoxon rank sum test. 90% confidence limits for the geometric mean ratio of the PK exposure parameters in the two groups of women will also be calculated.

For the first line TB drugs, a Stage 1 analysis similar to that described above will be performed but only after completion of the concentration assays following batch shipment. Since the TB drug samples will not be shipped and assayed in real time and the duration of TB drug treatment is time limited, the participant may no longer be receiving the TB drug being studied when the TB drug assay results become available. The PK analysis for the first line TB drugs will also include the Stage 2 approach described above, in which a within-participants comparison of TB drug PK exposure during pregnancy and postpartum will be performed, separately for HIV-infected and HIV-uninfected women in each study arm. Note that the sample size for this comparison may be less than the desired 25 evaluable women if some women complete their TB medication course before the postpartum visit where the PK sampling will be done. In addition, a Stage 3 between-participants comparison of first line TB drug PK exposure in HIV-infected versus HIV-uninfected women will be performed (using the two-sample Wilcoxon rank sum test) to assess whether exposure to first line TB drugs differs with vs. without concomitant ARV drug use and presence of HIV infection. Note that if a significant difference is observed in the between-participants analysis, it will not be possible to determine whether this difference is due to ARV use or HIV infection.

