## 5 Report Contents

Detailed descriptions of the content of each of the following sections are given in the AIP.

- 1) Maternal demographics summary
  - Race, ethnicity, and country
  - Age, gestational age, weeks after delivery and weight at PK visits
  - ARV/TB medication duration before antepartum visits; concomitant ARV/TB medications at antepartum visits
  - Viral load and CD4 at antepartum, delivery and postpartum visits
- 2) Maternal safety
  - List of AEs reported to Division of AIDS (DAIDS) as Expedited Adverse Events (EAEs)
  - List of Grade 3 or greater AEs
  - List of AEs that are possibly/probably/definitely related to study drugs, as determined by the Core Protocol Team and/or site investigators.
- 3) Maternal PK analysis (as applicable to study arm being analyzed)
  - PK descriptive summaries by parameter and study visit
  - PK parameter comparisons of antepartum vs. postpartum
  - Summary of mothers with AUC above 10th percentile in antepartum vs. postpartum
  - Summary of cord blood/maternal plasma ratio
- 4) Infant demographics
  - Birth weight, length, gestational age and most definitive HIV status
- 5) Infant safety
  - List of congenital anomalies
  - List of AEs reported to DAIDS as EAEs
  - List of Grade 3 or greater AEs
  - List of AEs that are possibly/probably/definitely related to study drugs, as determined by the Core Protocol Team and/or site investigators.
- 6) Infant PK analysis
  - Washout concentration and half-life summary

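### ARV plus first line TB arms: by default, women off TB drugs postpartum would stay in the Stage 2 ARV pairs, mixing the end of TB co-treatment into the pregnancy ratio

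*SAP*

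**What the plan says.** Two arms combine an ARV with first line TB treatment (SAP Section 2.1). Their primary objective (Section 2.3.1.2) is to describe, in pregnancy and postpartum, the PK of efavirenz or lopinavir/ritonavir and "first line TB drugs when co-administered as part of clinical care of HIV-infected pregnant women".

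For these arms, Table 1 in Section 4 lists a within-participant Stage 2 comparison, "Antepartum vs. postpartum ARV PK parameters". The row has no footnote. The first line TB-drug row, "Antepartum vs. postpartum TB drug PK parameter, separately for HIV+ and HIV"-negative women, carries the ** footnote, as does the second line TB-drug row. That footnote reads "This comparison may have a smaller sample size than 25 because some women may complete their TB treatment before the postpartum PK visit". The Section 4 text repeats the caveat for the first line TB drugs: "the sample size for this comparison may be less than the desired 25 evaluable women if some women complete their TB medication course".

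The analysis set is defined in Section 3: "Each analysis will include all participants with evaluable data for that analysis". A pharmacologist declares a participant's data unevaluable "if they do not have adequate pharmacokinetic evaluations to determine the pharmacokinetic exposure parameter of interest for that analysis". TB-drug status at the visit is not mentioned. The Stage 2 minimum of 12 women with postpartum measurements (Section 4) has no such condition either.

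Section 4 interprets the Stage 2 signed rank test and the 90% confidence limits for the geometric mean ratio as contrasting the pregnant with the non-pregnant state. For co-medication, Section 5 lists "concomitant ARV/TB medications at antepartum visits" and has no postpartum counterpart.

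**The concern.** A woman who has completed TB treatment has no postpartum TB-drug value, so she drops out of the TB-drug comparison by herself. The footnote correctly describes that as a smaller sample. Her ARV is another matter. If she still takes it and is adequately sampled, she has a valid postpartum ARV exposure, and nothing in the visible SAP removes her pair.

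That pair sets a value in pregnancy on TB drugs against a value postpartum off TB drugs. Two conditions change at once, and the plan names only one of them. The postpartum value also falls outside an objective about the drugs taken together. Section 2.1 makes the interaction between TB drugs and ARVs a study question, so the plan cannot assume that stopping TB drugs leaves ARV exposure unchanged. The postpartum count of women meeting the ARV AUC target (Section 2.3.1.2) is open to the same mixing.

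At stake is whether a primary comparison in these two arms describes pregnancy, or an unknown blend of pregnancy and the end of TB co-treatment. Enrolling more women would not remove such a bias.

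**Working it through.** **The plan's own figures.** The SAP states no power or precision for Stage 2, so there is no figure on this point to reproduce. Its one checkable statistic, the exact 80% limits for 6 of 25 in the Stage 1 monitoring rule (Section 2.5), reproduces as (0.131, 0.383) against the stated (0.13, 0.38). It does not bear on this point.

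**Inputs.**
- From the documents: a target of 25 women per arm; a minimum of 12 with postpartum measurements; 90% confidence limits.
- Not in the documents, so assumed: T, the ratio of ARV exposure with TB drugs to exposure without; f, the share of pairs off TB drugs postpartum; G, the true antepartum/postpartum ratio with TB drugs at both visits.
- Also assumed: T applies in full at the postpartum visit, and G is the same in women who finish and women who do not.

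**Formula.** A pair on TB drugs at both visits has expected log ratio log G. A pair off TB drugs postpartum has log G + log T. The average is

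(1 − f) log G + f (log G + log T) = log G + f log T,

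so the observed geometric mean ratio is G × T^f.

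**Results with no pregnancy effect (G = 1).**

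| T | f = 20% | f = 40% | f = 60% |
|---|---|---|---|
| 0.8 | 0.96 | 0.91 | 0.87 |
| 0.5 | 0.87 | 0.76 | 0.66 |
| 1.25 | 1.05 | 1.09 | 1.14 |

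For example, 0.8^0.2 = 0.96 and 0.5^0.4 = 0.76. With G = 0.75, T = 0.5 and f = 40%, the observed ratio is 0.75 × 0.76 = 0.57. If T = 1 or f = 0, the factor is 1.

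**Effect on inference.** A simulation of 2,000 runs per setting used n = 25, G = 1, T = 0.7, an assumed log-ratio SD of 0.3, two-sided alpha 0.10 and limits of 0.80 to 1.25. The SAP fixes none of the last three.

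| Pairs off TB drugs postpartum | Signed rank test rejects | 90% interval within 0.80–1.25 |
|---|---|---|
| 0 of 25 | 0.11 | 0.95 |
| 6 of 25 | 0.29 | 0.64 |
| 12 of 25 | 0.75 | 0.15 |

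**Pairs left after restriction.** Pairs on TB drugs at both visits number 25 × (1 − f): about 19 at f = 25% and 12 to 13 at f = 50%. They fall below 12 once f exceeds 1 − 12/25 = 52%. Within this set the expected ratio is G whatever T is.

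**The case against.** The strongest reply is that no sentence in the SAP says these women stay in. The ** footnote is correct where it stands, and its absence from another row is not an inclusion rule. The row is labelled as ARV with first line TB drugs, the objective concerns co-administration, and evaluability is judged separately for each analysis. A pharmacologist could decide that an ARV value off TB drugs is not the parameter of interest. Such handling, or the sampling schedule that decides whether these values arise at all, may be set out in the Protocol, the Pharmacokinetic SAP or the AIP, none of which was available for this review.

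Much of this stands. A reader might infer that the SAP prescribes a biased analysis; it does not say so. Retention is only the natural consequence of a rule based on sampling adequacy. But this SAP is the document that sets out the comparisons, and it anticipates TB completion without saying what follows for the ARV pairs.

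Three further inferences go too far:
- *That Stage 3 puts off-TB women in the wrong group.* Section 4 defines that group as ARV exposure with TB drugs and names no visit. The point arises only if postpartum values are used.
- *That the report would hide the problem.* Section 5 is an outline that leaves detail to the AIP. It can only be said that the listed contents do not require postpartum TB co-medication to be shown.
- *That the bias exaggerates a pregnancy effect.* The direction depends on T. Even with T below 1, a true ratio above 1 would be pulled toward 1.

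**Conclusion.** The point holds in a conditional form. Applied as written, the Section 3 rule would keep women who are off TB drugs postpartum in the Stage 2 ARV pairs of these two arms. The resulting ratio would then not isolate pregnancy under co-administration, which is what Section 2.3.1.2 and the Stage 2 interpretation call for. This is more than a missing detail, because following the rule changes what is estimated.

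The size is open. The multiplier T^f could be close to 1 or large enough to change the conclusion, and the documents fix neither T nor f. The figures above illustrate a range and do not estimate what happened in the study. Confidence is moderate. The point should be addressed because a primary objective is affected and the change is small.

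**What to change.** In Section 4 and Table 1:
- Base the main Stage 2 ARV comparison in the two first line TB arms on women receiving first line TB drugs at both visits. Show pairs off TB drugs postpartum as a separate stratum.
- Split the postpartum AUC target count in the same way.
- If postpartum values are used in Stage 3, include only women on TB drugs at that visit.
- Add the ** footnote to the Stage 2 row for ARV with first line TB drugs.

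In Section 5, add concomitant TB medication at the postpartum visit.

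The cost is wording, one split by TB-drug status and fewer pairs in the main estimate, as counted above. No extra enrolment is needed, and the minimum of 12 women with postpartum measurements can stay as it is. Report the number of on-TB pairs. Where too few remain for a meaningful comparison, give the estimate without a p-value, as Section 4.1 already allows. If the Protocol, the Pharmacokinetic SAP or the AIP already sets this rule, a cross-reference to it in Section 4 would be enough for the analysis set.

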## **2 Study Overview**

### **2.1 Overview of Study Design**

P1026s is a Phase IV, prospective pharmacokinetic (PK) study to evaluate the pharmacokinetics of selected currently prescribed antiretroviral (ARV) medicines when used alone or with tuberculosis (TB) medicines during pregnancy or with postpartum hormonal contraceptives in HIV-infected pregnant and postpartum women. The washout PK of transplacentally acquired ARV and TB drugs will be studied in the infants born to study mothers who enter the study during pregnancy. HIV-uninfected pregnant women receiving TB treatment (first line or second line) will also be enrolled to serve as a control group to evaluate the interaction between TB and ARV drugs in pregnant women.

Study Arm Groups (see arm details in Section 7 Attachment 1 and Protocol Schema):

- ARVs without TB Treatment (10 Arms)
- ARVs with First Line TB Treatment (2 Arms - one for each ARV drug)
- No ARVs with First Line Tuberculosis Treatment (1 Arm)
- Second Line TB Treatment for Drug-Resistant TB with or without ARVs (1 Arm)
- ARVs with Postpartum Contraceptives (4 Arms)

There is no randomization and stratification. Each study arm will enroll a minimum of 12 women and have a target enrollment of 25 women with evaluable 3rd trimester PK data in the ARV and TB arms, or evaluable postpartum PK data in the contraception arms. Enrollment may be restricted or adjusted so that 2nd trimester PK data are collected from at least 12 women. When combined enrollment in the increased dose darunavir arms reach 25 participants, the PK data will be evaluated to determine if the data for these arms can be combined and whether enrollment of additional participants in these arms should continue. Sample size for an ARV or TB drug arm may be increased if additional infants need to be enrolled to collect infant washout PK data. The

sample size of the second line TB drug arm may be increased above 25 to obtain additional data for less commonly used second line TB drugs.

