## 2.3 Study Objectives and Outcome Measures

This Primary SAP addresses the following primary and secondary objectives in the study protocol. Some secondary objectives were intended to be exploratory, and will be considered as “Other study objectives”. Therefore, this SAP will not include the outcome measures/analysis contents related to these exploratory objectives (see Section 2.3.2).

The study objectives below will be analyzed under an equivalence framework, including the comparisons between antepartum and postpartum PK parameters. The final analysis for each study arm will be done once the last participant for that arm has completed the last study visit and all queries have been resolved.

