## **2.4 Overview of Sample Size Considerations**

The sample size calculations will be based on assessing whether therapeutic dosing regimens for the study drugs produce adequate drug exposure during pregnancy as compared to historical data from non-pregnant adults.

Each study arm will enroll a minimum of 12 women and have a target enrollment of 25 women with evaluable 3rd trimester PK data for ARV and TB arms, or evaluable postpartum PK data for oral contraceptive arms. Women who do not have evaluable data will be replaced. Enrollment may be restricted or adjusted so that evaluable 2nd trimester PK data are obtained from at least 12 women. The sample size for an arm may also be increased if additional mothers and infants need to be enrolled to obtain evaluable infant washout PK data. Thus, the total number of participants enrolled per arm may be larger than 25 if women need to be replaced due to non-evaluable data, if additional women need to be enrolled to obtain 2nd trimester PK data, if additional mothers and infants need to be enrolled to obtain infant washout PK data and/or if additional women need to be enrolled to obtain enough second line TB drug data. When combined enrollment in the increased dose darunavir arms reaches 25 participants, the PK data will be evaluated to determine if the data for these arms can be combined and whether enrollment of additional participants in these arms should continue. The actual sample size will be based on the determination of PK exposure parameters, and whether or not the current dose provides adequate drug exposure to pregnant women.

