#### **4.1 Statistical Tests**

Within-participant comparisons (e.g., between pregnant versus non-pregnant conditions or second versus third trimester) will be performed for continuous outcome measures using the Wilcoxon signed rank test and for dichotomous outcome measures using McNemar's test. If the statisticians determine there are not enough women with PK data available at both time points for a meaningful comparison, then no p-value will be calculated. In addition, if there are no discordant pairs for McNemar's test, then the test will not be performed. Between-participant comparisons will be performed for continuous outcome measures using the Wilcoxon rank sum test and for dichotomous outcome measures using the chi-square or Fisher exact test.

90% confidence limits for the geometric mean ratio of the PK exposure parameter in the pregnant versus non-pregnant conditions will also be calculated to describe the range of values that are consistent with the observed data and help the Protocol Team assess whether there is a clinically important difference in exposure in the two conditions. The confidence coefficient will be 90% rather than 95% to match the usual practice in the pharmacokinetic literature to show that two conditions are sufficiently similar (e.g, bioequivalence testing).

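### The Stage 3 comparison of first line TB drugs in HIV-infected women on ARVs versus HIV-uninfected women has a rank sum test but no between-group ratio or interval, so a non-significant result would not show similar exposure

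*SAP*

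**What the plan says.** The HIV-uninfected women on TB treatment are enrolled "to serve as a control group to evaluate the interaction between TB and ARV drugs in pregnant women" (SAP section 2.1). Table 1 in section 4 lists the comparison that uses them, TB drug exposure with ARVs (HIV+) against without ARVs (HIV-), among those planned for the primary objectives.

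Section 4 describes two firmly planned Stage 3 comparisons in adjacent paragraphs:

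- **ARVs taken with first line TB drugs**, against earlier arms of the study without TB drugs. A rank sum test is planned, and "90% confidence limits for the geometric mean ratio of the PK exposure parameters in the two groups of women will also be calculated".
- **First line TB drugs**, with against without ARVs. The comparison in "HIV-infected versus HIV-uninfected women will be performed (using the two-sample Wilcoxon rank sum test) to assess whether exposure to first line TB drugs differs". No ratio or interval follows. The paragraph adds that a significant difference could not be attributed to ARV use rather than HIV infection. It does not say how a non-significant result will be read.

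Section 4.1 gives the general rule: "Between-participant comparisons will be performed for continuous outcome measures using the Wilcoxon rank sum test". Its interval sentence has a narrower scope: "90% confidence limits for the geometric mean ratio of the PK exposure parameter in the pregnant versus non-pregnant conditions will also be calculated". Section 2.3 says: "The study objectives below will be analyzed under an equivalence framework, including the comparisons between antepartum and postpartum PK parameters". No margin is given.

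**The concern.** A rank sum p-value tests for a difference. It does not say how large a difference the data allow, and a large p-value does not establish similarity. Yet similarity is what an equivalence framework addresses, and section 4.1 itself justifies the 90% level by the practice of showing that two conditions are sufficiently alike.

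At stake is what can be concluded about TB drug exposure in pregnant women who also take ARVs. If the test is non-significant, the planned output does not separate a small difference from a sample too small to tell. An interval would, and the SAP already plans one for the neighbouring comparison.

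**Working it through.** **1. Does another section supply the interval?**

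- Section 4.1: no. Its limits are tied to pregnant versus non-pregnant conditions. For between-participant comparisons it names tests only.
- Section 5 (report contents): no. It lists descriptive PK summaries and antepartum versus postpartum comparisons, but no with/without-ARV ratio.
- The within-woman analyses of second line TB drugs and of ARVs with contraceptives inherit the interval by pointing back to Stage 2. The Stage 3 text for first line TB drugs points back to nothing.

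**2. The plan's own figures.** The SAP states no power or precision for Stage 3. Its one operating figure, in section 2.5, concerns the Stage 1 rule: exact 80% limits for 6 of 25 of 0.13 to 0.38. This reproduces (0.131 to 0.383) but has no bearing on Stage 3.

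**3. How informative would a non-significant test be?**

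Inputs from the SAP: each arm has a minimum of 12 and a target of 25 (section 2.4). There are two HIV-infected first line TB arms and one HIV-uninfected arm (section 2.1).

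Assumptions, because the documents give none: between-woman CV 30% to 70%, true ratio 0.75, two-sided 5% level, log-normal exposure.

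Formulas:

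- σ = √ln(1 + CV²)
- SE = σ·√(1/n₁ + 1/n₂)
- noncentrality δ = |ln 0.75| / SE = 0.288 / SE
- power from the noncentral t distribution with n₁ + n₂ − 2 degrees of freedom

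Example, CV 50%, 25 v 25: σ = √ln 1.25 = 0.472; SE = 0.472 × √0.08 = 0.134; δ = 2.15; power 0.56.

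| CV | Women (ARV v no ARV) | SE | δ | Power at ratio 0.75 |
|---|---|---|---|---|
| 50% | 12 v 25 | 0.166 | 1.73 | 0.39 |
| 50% | 25 v 25 | 0.134 | 2.15 | 0.56 |
| 50% | 50 v 25 (ARV arms pooled) | 0.116 | 2.49 | 0.69 |
| 30% | 25 v 25 | 0.083 | 3.46 | 0.92 |
| 40% | 25 v 25 | 0.109 | 2.64 | 0.73 |
| 60% | 25 v 25 | 0.157 | 1.83 | 0.44 |
| 70% | 25 v 25 | 0.179 | 1.61 | 0.35 |

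The t approximation is slightly generous to the rank sum test. At CV 50%, 25 v 25 and a true ratio of 0.80, it gives 0.37, against 0.34 by simulation of the rank sum test itself (4,000 runs).

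**4. What the interval would add.** Take CV 50% and an observed ratio of 0.80.

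- 25 v 25: t = 0.223/0.134 = 1.67, p about 0.10. The 90% limits are 0.80 × exp(±1.677 × 0.134), that is 0.64 to 1.00.
- 12 v 12: p about 0.26, limits 0.57 to 1.11.

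Both results are non-significant at 5%. Only the limits show that a reduction of 36% (1 − 0.64) or 43% (1 − 0.57) is not excluded. With an observed ratio of 1.0 and 25 v 25, the limits would be 0.80 to 1.25.

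**The case against.** Several points on the other side are sound.

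- **A reader might infer that the comparison will produce nothing but a p-value.** The documents do not support that. Section 3 requires mean, median, SD, interquartile range and range, section 5 lists PK summaries by parameter and visit, and section 2.3.1.2 counts women who meet the C<sub>max</sub> target. Section 4.1 allows chi-square or Fisher tests for dichotomous measures. What is missing is narrower: a between-group ratio with its uncertainty.
- **A reader might infer that this comparison is the sole reason for the HIV-uninfected arm.** Section 2.1 does call it a control group, but the objective in section 2.3.1.2 is descriptive and names HIV-uninfected women separately. Section 2.2 records that there is no hypothesis.
- **A reader might infer that a null result will be reported as no ARV effect.** No section says so, and the equivalence framework points the other way. This is a risk left open, not a stated plan.
- **Power depends on the assumed CV and on pooling.** At CV 30% with 25 per group it is high. The SAP does not say whether the ARV arms are pooled, and section 2.4 allows arms to exceed 25. The gap remains all the same, since good power does not turn a p-value into an estimate.
- **Other documents may cover it.** The protocol text, the separate Pharmacokinetic SAP and the AIP were not available. But section 4 says that this SAP defines the PK comparisons done by the statisticians, so the interval belongs here.
- **An interval cannot separate ARV use from HIV infection.** That is true, and section 4 says as much about a significant difference. The ratio must be labelled accordingly.

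**Conclusion.** The point holds as a gap in this SAP. The Stage 3 comparison of first line TB drugs has a named test and no ratio or interval, although the adjacent ARV comparison has both and section 2.3 sets an equivalence framework. It may be no more than a drafting omission.

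The consequence is limited to how a non-significant result can be read. For a true ratio of 0.75, such a result would occur in about 44% of studies (1 − 0.56) at CV 50% and 25 v 25. This runs from about 8% at CV 30% to 56% at CV 60%. At CV 50% it is about 61% with 12 v 25 and 31% with 50 v 25. The CV, the ratio and the 5% level are assumptions; the arm sizes are the SAP's.

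The change should be made: it is nearly free and alters what the comparison can support. It does not imply that any planned number is wrong.

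**What to change.** In SAP section 4, extend the interval sentence of the ARV Stage 3 paragraph to first line TB drugs. Suggested text:

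> For the Stage 3 comparison of first line TB drugs, the geometric mean ratio (HIV-infected with ARV / HIV-uninfected without ARV) and its 90% confidence limits will be calculated for each PK parameter and visit, by ARV arm, and pooled if the arms are combined. The ratio describes ARV use and HIV infection jointly. A non-significant rank sum test will not be taken as evidence of no difference.

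Apply the same to any second line TB drug Stage 3 comparison that is performed, and widen the interval sentence in section 4.1 to match. If the team wishes to conclude that exposure is similar, rather than only report the limits, it also has to state beforehand the range of ratios that it regards as unimportant; the SAP gives none.

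Cost: a few lines of SAP text and one extra column of output. No new data, samples or visits are needed.
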